Pilot Arm – active arm but completed post-screening (i.e. offsite on own device)

Inferences about the effect of the Health4Her intervention completed post-screening (i.e. offsite on own device) on outcomes will be based on based on: 1) a comparison of change, in the pilot arm only, from baseline to immediate post-intervention (i.e. immediately post-randomisation) and/or 4-weeks post-randomisation, and 2) a comparison, between treatment groups (i.e. pilot arm vs control; pilot arm vs intervention; acknowledging that assignment to the pilot arm was not randomised), of change from baseline to immediate post-intervention (i.e. immediately post-randomisation) and/or 4-weeks post-randomisation. The analytic methods described above will be implemented here.

Missing data

Where appropriate, missing values will be addressed through maximum likelihood estimation (i.e. in a mixed model) or using multiple imputation.

Sensitivity analyses

Several sensitivity analyses may be performed:

- Using a per-protocol approach, defined as those who received all elements of the intervention.

- Stratified by participants based on those who: a) report drinking any alcohol in the past month, and b) are identified to be drinking at a level exceeding current national guidelines for weekly and/or single day consumption.
- Including relevant covariates (e.g. age, education, CALD, LGBTIQ+A+) as adjustments. Covariates may also be used to stratify analyses.
- Models to examine the robustness of missing data modelling decisions (e.g. including auxiliary variables in models or in complete case data).

Primary Outcome

- 1) Change in next-month drinking intentions (immediate post-intervention)

Secondary Outcomes

- 1) Change in next-month drinking intentions (4-weeks post-randomisation)
- 2) Change in intended number of standard drinks consumed over the next month (4-weeks post-randomisation)
- 3) Proportion of participants intending to reduce their next-month alcohol consumption (immediate post-intervention)
- 4) Proportion of participants intending to reduce their next-month alcohol consumption (4-weeks post-randomisation)
- 5) Proportion of participants accurately identifying alcohol as a clear risk factor for breast cancer (4-weeks post-randomisation)

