4.2 RANDOMISED CONTROLLED TRIAL OF H4H-A

Study design: A single site, double-blind, parallel-group randomised controlled trial, comprising baseline and 4-week follow-up assessments.

Setting and participants: This trial will aim to recruit at least 78 participants (39 per trial arm). Women attending Maroondah BreastScreen for routine mammography (throughput ~65/screening day), aged 40+ years, with or without a breast cancer history, and drinking at any level of alcohol consumption will be eligible to participate after they complete their screening appointment. **Exclusion criteria:** Women not able to read or comprehend English to enable participation, or who do not have access to computer, tablet or smartphone to complete the follow-up assessment, will be excluded from this iteration of the research. Women who are pregnant will be excluded (also an exclusion of breast screening). Women who participated in the previous Health4Her study will also be excluded (a woman can provide her name to the recruitment researcher for cross-checking against the previous participant list if she is unsure of previous participation. The same recruitment researcher that was onsite for the previous study will be onsite for this study. The researcher will exercise care to ensure security and privacy measures are used, i.e. the list will only include name and year of birth; the list

will be hosted on a secure server managed by Monash University eSolutions and accessible to only the recruiting researcher via a secure login; the list will never be shown to potential participants).

Recruitment: Maroondah BreastScreen reception staff will provide a reminder text message one day prior to recruitment days to flag the study occurring onsite (as well as serving to confirm appointment attendance). Upon arrival at Maroondah BreastScreen, the receptionist will query whether women are aware of the study and provide them with a study flyer to read while waiting for their appointment. Study posters will also be visible on the waiting room notice board and in the screening rooms. At the end of the screening appointment, the radiographer will ask whether the client would like to hear more about the study from the onsite researcher / be involved, and if the client agrees or has further questions, the radiographer will introduce the client to Researcher 1.

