Randomisation, interventions and procedure: The study will be described as the “Health4Her women’s health study” to minimise the salience of the trial’s alcohol focus, and to increase its relevance for all women. In the active and control arms, participants will be provided with an iPad and earbuds, and will self-complete consent (via a landing page) and baseline assessment before being randomly assigned (1:1 allocation ratio, utilising a “permuted blocks of variable size” scheme embedded in the iPad) to receive 1) ~4 minutes of alcohol brief intervention plus ~3 minutes of lifestyle information (active arm: H4H-A), or 2) ~3 minutes of lifestyle information not inclusive of alcohol information (control arm) via interactive animation. An assessment immediately post-intervention will be completed on the iPad (comprising only the set of intention questions containing the primary outcome item). A 4-week follow-up assessment will be completed offsite via online survey, with the follow-up researcher prompting/assisting with survey completion when required.

Alcohol brief intervention (active arm): Finalised through the collaborative design process, and based on brief intervention and applied behaviour change principles, the alcohol brief intervention will include information and behaviour-change content regarding alcohol consumption such as: messaging around alcohol risks/harms, positive-framed messaging on the health benefits of reducing alcohol intake, and behaviour change strategies (e.g. drink counting, goal setting, behaviour substitution, problem solving) (12, 23-26). This iteration of the research provides an opportunity to refine and add to the evidence-based intervention elements utilised in the pilot (e.g. provide the intervention in ‘chunks’, where the participant will view 1-2 minutes of animation before completing a brief activity such as setting goals or problem solving strategies), with the goal of strengthening intervention response. **NB.** H4H-A will be aligned with the National Health and Medical Research Council’s recently revised Australian Alcohol Guidelines (i.e. no more than 10 standard drinks per week, with the message ‘the less you drink, the lower your risk of alcohol-related harm’). Post-session information will be provided via email (i.e. an electronic brochure summarising alcohol brief intervention content).

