While this study will examine reach, uptake, feasibility and acceptability as important end-points, it will be powered to test the effectiveness of H4H-A in decreasing women's drinking intentions. The sample size has been calculated using data from a previous, related study examining the effects of alcohol warning information about the alcohol-breast cancer link on drinking intentions (15). Using a Likert 5-point response scale (1 = not at all, 5 = to a very great extent, this study showed that the warning information, *Alcohol increases your risk of breast cancer*, increased participants' intention to reduce the amount of alcohol they consume from a pre-exposure mean of 2.37 (SD = 1.18) to a post-exposure mean of 2.63 (SD = 1.22).

Given some differences in the previous study (i.e. the message about alcohol and breast cancer risk was not personally relevant to the whole sample comprising males and females 18-65 years; a single health message was provided, which is different to the Health4Her intervention containing several 'active ingredients' based on alcohol brief intervention and applied behaviour change principles), we anticipate a greater increase in participants' intention to reduce the amount of alcohol they consume in the current study. Further, based on our previous research, we anticipate some assessment reactivity among the control group.

Power and sample size estimations were conducted using General Linear Mixed Model Power and Sample Size (GLIMPSE) software. We estimate (factoring in 5% attrition, and 30% of women attending breast screening who do not drink or have not drunk in the past month) that a total sample size of at least 78 (39 per group) will have 80% power ($\alpha < 0.05$) (a total sample size of 90 [45 per group] will provide 85% power, $\alpha < 0.05$) to detect a change in women's drinking intentions of 2.37 to 3.37 (change = 1.00) in the intervention group, and a change of 2.37 to 2.63 (change = 0.26) in the control group between baseline and immediately post-intervention. Therefore, this study will aim to recruit a total

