sample size of at least 78 participants. Based on the barriers to participation and implementation identified in the previous phase of this research, the current study will provide an opportunity to collect some pilot data to inform scaled up research and implementation, to provide an indicator of outcomes for participants who complete a modified version of the alcohol brief intervention offsite using their own personal device (n~20).

Statistical analyses: A full Statistical Analyses Plan will be developed prior to trial commencement. All statistical tests will be two-tailed, with the alpha level set to 0.05 and analyses conducted using the most appropriate procedures in Stata or R. All randomised participants will be included in the analyses (i.e. intention-to-treat) for primary and secondary outcomes. Analyses will examine change in outcomes over time (baseline, immediately post-intervention, 4-weeks). For intention outcomes, we will examine differences in responses according to baseline alcohol consumption risk status (i.e. drinking at a level within/exceeding current national alcohol guidelines). For alcohol outcomes, sensitivity analyses will be performed for women who a) report drinking any alcohol in the past month, and b) are identified to be drinking at a level exceeding current national guidelines for weekly and/or single day consumption. The Generalised Linear Mixed Model approach with fixed effects for treatment and time, and their interaction, and random effects for subjects and assessments within subjects, will be applied to examine the treatment effect of the intervention on all outcomes.

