6 STUDY PROCEDURES

6.1 STUDY FLOW CHART

6.2 SCHEDULE OF ASSESSMENTS

| Assessment | Time point: | Pre-trial | Maroondah BreastScreen | | Online survey |
|--|-------------|-----------|-------------------------------------|--------------------------------------|----------------------------------|
| | | | 0 (immediately pre-intervention) | 1 (immediately post-intervention) | 2 (4-weeks post-intervention) |
| COLLABORATIVE DESIGN OF H4H-A | | | | | |
| In-person and online workshops with breast screening service consumers | | x | | | |
| IMPLEMENTATION OF H4H-A^a | | | | | |
| Eligibility assessment (breast screening staff will assess English comprehension; question about access to computer, tablet or | | | x | | |

| | | | | |
|---|--|---|-----------------------------|-------------|
| smartphone embedded at start of intervention) | | | | |
| Trial explanation (embedded at start of intervention) | | x | | |
| PIS (link embedded at start of intervention, and emailed) | | x | | |
| Informed consent (embedded at start of intervention) | | x | | |
| Randomisation | | | x | |
| Intervention | | | x | |
| Measures | | | | |
| Primary outcome | | | | |
| Drinking intentions (5-point Likert scale) | | x | x | x |
| Secondary outcomes | | | | |
| Drinking intentions (QF intentions) | | x | | x |
| Alcohol-breast cancer literacy | | x | | x |
| Alcohol literacy | | x | | x |
| Alcohol consumption (past-month QF) | | x | | x |
| Knowledge of other breast cancer risk factors | | x | | x |
| PROGRAM EVALUATION ^a | | | | |
| Trial / service administrative data collection | | | (throughout implementation) | |
| Participant feedback | | | | (end trial) |
| Site staff and manager feedback | | | | (end trial) |

^a Participants in the modified active arm being piloted will participate in eligibility assessment, informed consent, baseline, intervention, follow-up and program evaluation in the same way as participants in the active / control arms, but will not be randomised and will complete all activities offsite.

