7.2.5 ALCOHOL CONSUMPTION

Alcohol consumption will be measured using adapted versions of alcohol frequency/quantity items used in national alcohol intake surveys (40), i.e. frequency of alcohol consumption during the past month (categorical response item), and type/number of drinks consumed on a typical drinking day during the past month (visual drag and drop item). A composite value will be calculated from responses to these items, estimating standard drinks consumed during the past month. This composite value will also be used to inform which normative feedback is provided in the brief intervention.

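### The main model for all randomised women has no baseline drinking-status term, which gives up modest precision that data already collected before allocation would recover

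*Combined protocol and SAP*

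**What the plan says.** **Who is in the analysis.** Under Setting and participants, protocol 4.2 states that women "drinking at any level of alcohol consumption will be eligible to participate". The power paragraph allows for "30% of women attending breast screening who do not drink or have not drunk in the past month". The Statistical analyses paragraph keeps all randomised women in the primary and secondary analyses.

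**What is known before allocation.** Women complete consent and the "baseline assessment before being randomly assigned (1:1 allocation ratio" is stated next, with the scheme, "permuted blocks of variable size", held on the same iPad). The schedule in 6.2 lists "Alcohol consumption (past-month QF") as a pre-intervention measure. Section 7.2.5 says of the derived drinks total: "This composite value will also be used to inform which normative feedback is provided in the brief intervention". Neither document names a stratification factor.

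**What the model contains.** SAP, Analytic approach, and protocol 4.2, Statistical analyses, give the same terms: fixed effects for treatment, time and their interaction, with random effects for subjects and for assessments within subjects. SAP, Sensitivity analyses, lists among analyses that may be done: "Including relevant covariates (e.g. age, education, CALD, LGBTIQ+A+) as adjustments". Drinking status is not among those examples. The bullet before it offers analyses stratified by past-month drinking and by exceeding national guidelines. For intention outcomes, protocol 4.2 adds that "we will examine differences in responses according to baseline alcohol consumption risk status".

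**The concern.** The primary item (7.2.1) asks how far a woman intends to reduce her drinking over the next month, scored 1 to 5. A woman who has not been drinking has little to reduce, so her score should hardly move in either arm. Mixing such women with drinkers adds between-group spread to the change scores. A model without drinking status counts that spread as noise in the arm-by-time contrast.

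At stake is efficiency in a trial of 78 women planned at 80% power. There is also a pre-specification issue: whether to adjust for an obviously relevant baseline factor is left open until after the data are seen.

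**Working it through.** **Inputs from protocol 4.2.** 39 per arm; drinkers change by 1.00 (intervention) and 0.26 (control); SDs 1.18 before and 1.22 after; 30% not drinking; two-sided alpha 0.05.

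**Assumed.** Pre-post correlation ρ of 0.5, 0.7 or 0.8 (not in the documents); the planned changes apply to drinkers; women not drinking have zero change; no attrition.

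**1. The plan's own figure.** Variance of change = 1.18² + 1.22² − 2ρ(1.18)(1.22) = 2.8808 − 2.8792ρ. At ρ = 0.70 this is 0.865 (SD 0.930). For a difference of 1.00 − 0.26 = 0.74, 80% power needs 26 evaluable women per arm, and 52/(0.70 × 0.95) = 78.2. Power is 80.2% at 78 and 85.7% at 90, which matches the plan. Without the 30% and 5% allowances, ρ of about 0.53 gives 79.2% and 84.7%, so the documents do not settle which inputs were used. The argument below does not depend on this.

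**2. All-randomised contrast, no status term.** The expected difference is 0.70 × 0.74 = 0.518. With 70% drinkers, the variance of change in an arm is 0.70σ² + 0.70 × 0.30 × (drinkers' mean change)². At ρ = 0.70:
- intervention: 0.606 + 0.21 × 1.00² = 0.816
- control: 0.606 + 0.21 × 0.26² = 0.620
- SE = √[(0.816 + 0.620)/39] = 0.192
- power = Φ(0.518/0.192 − 1.96) = 0.77

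**3. With a status term in the change model.** The pooled drinker effect is (1.00 + 0.26)/2 = 0.63, which leaves ±0.37 unexplained among drinkers in each arm. Variance per arm = 0.606 + 0.21 × 0.37² = 0.634. Allowing for the chance imbalance that the term must absorb, by a factor of about 1 + 1/75, SE = √[2 × 0.634/39 × 76/75] = 0.182 and power is 0.81.

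| ρ | σ² of change | SE without | SE with | Variance removed | Power |
|---|---|---|---|---|---|
| 0.5 | 1.441 | 0.240 | 0.232 | 6% | 0.58 to 0.61 |
| 0.7 | 0.865 | 0.192 | 0.182 | 10% | 0.77 to 0.81 |
| 0.8 | 0.577 | 0.163 | 0.150 | 15% | 0.89 to 0.93 |

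Simulation of the same set-up (6,000 trials per ρ) gave SEs of 0.240 v 0.234, 0.192 v 0.182 and 0.163 v 0.151, so about 5%, 10% and 14% of variance. Power went from 0.57 to 0.61, 0.76 to 0.82, and 0.89 to 0.94.

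**4. If women not drinking do vary.** Give their change an SD of 0.5, which adds 0.30 × 0.25 = 0.075 to each arm's variance. The same formulas remove 6%, 9% and 13% of variance. Power goes from 0.55 to 0.58, 0.73 to 0.77, and 0.84 to 0.89.

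**5. Why the interaction with time is needed.** The contrast is a difference in changes. A status main effect adds the same amount to a woman's score at every visit and cancels when baseline is subtracted. With complete data and a random intercept it leaves the arm-by-time estimate unchanged. The status term in step 3 corresponds to status-by-time in the repeated-measures model.

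**6. Would stratified allocation add more?** In simulation with blocks of 2, 4 and 6 at ρ = 0.70, the SE was 0.192 with neither stratification nor adjustment, 0.183 with stratification alone, and 0.184 with adjustment alone. At ρ = 0.55 the three were 0.229, 0.222 and 0.223.

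**The case against.** **The plan already handles drinking status.** It commits to examining intention outcomes by risk status, it offers an analysis of past-month drinkers, and its sample size allows for the 30%. Under the same assumptions, the drinkers-only analysis has power of 0.60, 0.81 and 0.94, the same as the adjusted model. The covariate list is also open-ended. All of this is true. But the risk-status split is within v exceeding guidelines, not any v none. The drinkers-only analysis is a sensitivity analysis that the SAP says may be done, and it answers a question about a different population. Neither changes the main contrast in all randomised women.

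**The gain rests on assumptions.** It does. The correlation is not stated. The 30% covers women who have not drunk in the past month, some of whom may drink at other times and hold real intentions, so it is wider than non-drinkers. More variable responses in that group shrink the gain, though step 4 shows that it survives an SD of 0.5.

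**Stronger readings that do not hold.** A reader might infer that the randomisation is at fault because it ignores a factor the iPad has just recorded. The documents do not support that. Permuted-block 1:1 allocation is valid and unbiased, the documents are silent on strata rather than ruling them out, and step 6 shows that adjustment recovers nearly all the precision.

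A reader might also infer that the planned drinking subgroups are compromised and that any v none strata would repair them. Among past-month drinkers (about 55 women) mean relative efficiency is 0.994, so almost nothing is lost. The smaller group exceeding guidelines can be lopsided. If 20% exceed (an assumed share), the arms differ by 4 or more in about 32% of trials. Stratifying by any v none only lowers this to about 28%.

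**Conclusion.** The point stands as a modest efficiency and pre-specification gap in the SAP's main model. It is not a flaw in the allocation. Omitting status-by-time costs about 5 to 14% of the variance of the all-randomised primary contrast, or roughly 2 to 5 power points. That assumes ρ between 0.5 and 0.8, the planned changes applying to drinkers, and little or no change among the 30% who have not drunk in the past month. Every value tried gives a gain. There is no bias, and the main analysis remains valid as written.

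**What to change.** In SAP, Analytic approach, pre-specify baseline past-month drinking (any v none, from the 7.2.5 items) and its interaction with time as fixed effects in the main model for the primary outcome and for the alcohol outcomes analysed in all randomised women. State that this is the main analysis and not a sensitivity analysis. For past-month consumption, hypothesis 3.1(h) is already limited to women who drank in the past month, so the term drops out there.

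**Cost.** One sentence, with no extra data or participants. The interaction uses one degree of freedom for outcomes with two time points and two for the three-point intention item, plus one for the main effect. For the yes/no intention outcome the term may not be estimable if almost no woman in the not-drinking group reports an intention to reduce, so the SAP should name a fallback.

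Stratifying the iPad's blocks by the same item is an optional extra only if allocation has not begun. The SAP's Study rationale and design section, finalised 7 Feb 2024, describes randomisation in the past tense, which suggests that it has. Stratification would mean two block lists in place of one and would add almost no precision beyond adjustment. It should not be presented as the remedy for the subgroup exceeding guidelines.

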Statistical Analysis Plan (SAP)

This plan, or SAP Addendum, provides additional detail to the statistical considerations that were documented in the statistical analysis plan in Health4Her-Automated Protocol_V4_11 08 2023 (available via the [trial record](#) on ClinicalTrials.gov).

Additional analyses not specified in the published protocol or this addendum will be regarded as exploratory.

Statistical software

Analyses will be conducted using the most appropriate procedures in programs such as GenStat, R, SAS, or Stata.

Analytic approach

Data will be collated, cleaned, and validated using programmed edit checks.

The analysis will take place based on the intention to treat (ITT) principle (i.e. subjects' data are analysed as randomised) after all subjects, not known to have withdrawn or not deemed lost to follow-up, have had their 4-week assessments.

Outcome variables with repeated measurements will be analysed by fitting Generalised Linear Mixed Models (GLMMs) with an appropriate link function (e.g. gaussian for continuous outcomes or outcomes treated as continuous [e.g. 5-point Likert scales] and logit for binary outcomes). Inferences about the effect of the Health4Her intervention on the outcomes will be based on a comparison, between treatment groups, of change in outcomes from baseline to immediate post-intervention (i.e. immediately post-randomisation) and/or 4-weeks post-randomisation. Models will estimate fixed effects for treatment and time, and their interaction, and random effects for subjects and assessments within subjects. If necessary, suitable variance-covariance structures for the repeated measures will be compared using Akaike's Information Criterion and/or Bayesian Information Criterion. In the case that GLMMs have estimation/convergence difficulties regression models may be estimated via Generalised Estimating Equations (with an appropriate link function). A Wald test (or equivalent approach) will be used to test for an overall group by time interaction in outcomes.

Outcome variables without a baseline assessment will be examined using Generalised Linear Models (i.e. the non-mixed model version). Inferences about the effect of the Health4Her intervention on these outcomes will be based on a comparison between treatment groups of outcomes assessed at 4-weeks post-randomisation. Models will estimate fixed effects for treatment.

All statistical tests will be two-tailed with the alpha level set to 0.05.

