- g) *Change in alcohol literacy*: we hypothesise that there will be a greater change in the proportion of intervention participants, relative to control participants, accurately identifying the i) the increased breast cancer risk associated with drinking one average restaurant serve of wine a day; ii) number of standard drinks in an average restaurant serve of red wine; iii) maximum number of standard drinks per week recommended by current Australian Alcohol Guidelines between baseline and 4-weeks.
- h) *Change in alcohol consumption*: among women who have had an alcohol drink in the past month, we hypothesise that there will be a greater reduction in alcohol consumption among intervention participants relative to control participants, between baseline and 4-weeks.
- i) *Change in knowledge of other breast cancer risk factors*: we hypothesise that, in both intervention and control arms, there will be a significant increase in the proportion of participants accurately identifying inactivity and excess weight as risk factors for breast cancer between baseline and 4-weeks. (This represents a potential value-add of the intervention among women in the control group, and those who do not drink alcohol).

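### Does the stated 80%/85% power describe drinkers only, while the primary analysis takes all randomised women?

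*Combined protocol and SAP*

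**What the plan says.** In protocol section 4.2, the power paragraph states that a "total sample size of at least 78 (39 per group) will have 80% power", with 85% at 90 (45 per group), to detect a change of 1.00 in the intervention group against 0.26 in controls. The calculation is described as "factoring in 5% attrition, and 30% of women attending breast screening who do not drink or have not drunk in the past month".

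The trial population is broader than drinkers. Women "drinking at any level of alcohol consumption will be eligible to participate", and hypothesis (i) in section 3.1 mentions a benefit "among women in the control group, and those who do not drink alcohol". The protocol's analysis paragraph says "All randomised participants will be included in the analyses (i.e. intention-to-treat) for primary and secondary outcomes", and the SAP's analytic approach agrees: "The analysis will take place based on the intention to treat (ITT) principle".

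On subgroups, the protocol has two adjacent sentences: "For intention outcomes, we will examine differences in responses according to baseline alcohol consumption risk status", and then "For alcohol outcomes, sensitivity analyses will be performed for women who a) report drinking any alcohol in the past month". The SAP's list of sensitivity analyses includes stratification by past-month drinking without restricting it to particular outcomes, but introduces the whole list as optional.

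**The concern.** An allowance of 30% listed next to attrition normally means that those women were taken out of the analysable number. On that reading the calculation concerns about 26 drinkers per group at N=78, and 0.74 is the drinkers' effect. The planned analysis puts the other women back. A woman who does not drink has little to reduce, so including her should shrink the average difference, and the stated 80% would then be too high for the primary analysis.

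A second worry follows. If the all-randomised effect is diluted, the drinkers-only result is the natural supporting evidence. The protocol commits to it for alcohol outcomes but treats intention outcomes in a separate sentence, and the SAP makes it optional. The drinkers' result for the primary outcome could then be shown or left out once the data are known.

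**Working it through.** **Inputs (protocol 4.2).** Difference in change 1.00 - 0.26 = 0.74; SDs 1.18 (pre) and 1.22 (post) from the earlier warning-message study; two-sided 0.05; attrition 5%; non-drinkers 30%. The pre/post correlation ρ is not given, so it has to be solved for.

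**Analysed numbers per group.**
- After attrition: 39 × 0.95 = 37.05 and 45 × 0.95 = 42.75, so about 37 and 43.
- Drinkers after attrition: 37.05 × 0.70 = 25.9 and 42.75 × 0.70 = 29.9, so about 26 and 30.

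**Method.** Two-sample t test on change scores (noncentral t), with SD of change = √(1.18² + 1.22² - 2ρ × 1.18 × 1.22).

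**Reproducing the plan's figures.** For each reading, ρ is set to give 80% at the smaller size, and power at the larger size is then a check.

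| Reading | Difference | n per group | ρ for 80% | Power at larger size |
|---|---|---|---|---|
| Drinkers only | 0.74 | 26 / 30 | 0.698 (SD of change 0.934) | 85.5% |
| All women, 0.74 already their average | 0.74 | 37 / 43 | 0.564 (SD of change 1.121) | 85.7% |
| All women, 30% used as dilution | 0.70 × 0.74 = 0.518 | 37 / 43 | 0.751 to 0.788 | 85.7% |

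The range in the last row covers a non-drinker change SD of 0 to 0.5. All three readings fit both stated figures, so the arithmetic cannot tell which was used.

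**Size of the loss if the drinkers-only reading is right.** Suppose the 30% have zero mean change with SD k. The variance of change in an arm is 0.70 × 0.934² + 0.30k² + 0.21μ², where μ is the drinkers' mean change (1.00 or 0.26).
- k = 0: arm variances 0.611 + 0.210 = 0.821 and 0.611 + 0.014 = 0.625; average 0.723, SD 0.850. With difference 0.518, power is 73% at 37 per group and 80% at 43.
- k = 0.5: add 0.075 to each variance; SD 0.893. Power is 69% and 76%.
- Extreme case, k = 0.93: power is 60% and 67%.

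**Sensitivity to the zero-response assumption (37 per group).** The 30% includes women who drink but did not in the past month, so a zero effect in all of them is pessimistic.
- A quarter respond as drinkers do (22.5% do not): difference 0.775 × 0.74 = 0.574; power 76% (k = 0.5) to 79% (k = 0).
- Half respond (15% do not): difference 0.85 × 0.74 = 0.629; power 83% to 84%.

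**Drinkers-only analysis.** Hypothesis (h) in section 3.1 already limits the consumption outcome to women who drank in the past month. A past-month-drinkers sensitivity analysis of consumption alone would therefore add nothing, so the protocol's alcohol outcomes must reach further, most naturally to drinking intentions. The SAP describes itself as adding detail to the protocol, and it does not cancel the protocol's commitment. For the guideline split, the protocol gives a weekly ceiling of 10 standard drinks, and zero lies within it.

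**The case for a change.** The strongest case for acting is that the drinkers-only reading is the most natural one, and that the protocol limits an outcome to drinkers when it means to (hypothesis (h)) but does not do so for the primary hypothesis. A power figure that fits three different populations cannot be checked. No section says how a non-drinker's answer to the intention item is handled. Naming the population and making the SAP's wording firm would cost only a few words, and past-month drinking is recorded before randomisation, so the subgroup is sound.

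Most of these observations stand as description: the population and the correlation are missing, and the SAP is looser than the protocol. The inference to a wrong power does not stand. The 69-73% needs a back-solved correlation, an assumed zero effect in the whole 30%, and an assumed spread for those women; none is in the documents. A much lower figure, about 50% at N=78, arises if 0.74 was run on 37 per group (SD of change 1.12) and then diluted to 0.518. That requires the 30% to have been left out, and the protocol says it was factored in. Conversely, if non-drinkers gave no usable score, a likelihood-based mixed model would in effect analyse drinkers and the stated power would apply, although the all-randomised wording weighs against this.

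**Conclusion.** No change to the plan follows. The 80%/85% cannot be verified from the documents, but it is not shown to be wrong. A shortfall of about 7 to 11 points at N=78 (80% down to 69-73%) depends on 0.74 being the drinkers' difference and on no effect at all in the other 30%; it is gone if half of them respond as drinkers do, and absent on the other two readings.

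The primary population is fixed as all randomised women in both documents, the type I error is untouched, and a null result can be read from its confidence interval. The figure of 78 is a stated minimum. The SAP describes randomisation and follow-up in the past tense, so relabelling the power would document the design without altering it.

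The drinkers-only analysis is best read as already promised by the protocol for intentions. Analysts following both documents would run it as supporting evidence, with less precision: a 95% interval half-width of about 0.52 for 26 drinkers per group, against 0.39 to 0.41 for 37 randomised women per group (SD of change 0.934 in drinkers). The optional wording in the SAP is a minor mismatch about a supporting analysis and does not bear on the trial's primary conclusion.
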